4.4 Study Variables

4.4.1 Summary of study data and timing of measurements

The study measured patients at the following timepoints:

- Screening
- Pre-operative mechanistic visit
- Day of the operation

- Early mechanistic post-operative visit 1-2 weeks after operation
- Late mechanistic post-operative visit at 20% total body weight loss of the preoperative value
- 3 months post-operatively
- 6 months post-operatively
- 12 months post-operatively

Table 1 outlines the key study measurements, and the timing of these measurements.

	Screening visit	Pre-op visit	Operation	Early mechanistic post-op visit	Late mechanistic post-op visit	3, 6 months post-op	12 months post-op
Demographics, duration of T2DM	Х						
Weight/weight loss, BMI			х			Х	х
HbA1c			х			х	х
Other blood tests			Х				х
BP /heart rate	х	Х		х	х		х
Body composition and measurements, BMR	x	Х		x	X		х
Comorbidities and King's Score	х						Х
Medications			Х			Х	х
Food diary		Х		Х	Х		
Rates of T2DM remission							Х
Bowel movements							х
GLP-1, GIP, PYY, bile acids, FGFs		Х		X	х		
Fasting Plasma Glucose		Х	x	x	х		х
Postprandial plasma glucose		Х		х	х		
Markers of insulin secretion		Х		х	х		
Ra, Rd, MCR from Clamp		Х		x	х		
VAS		Х		Х	Х		
Microbiota, metabolomics		Х		X	Х		
Faecal calories		Х					х
Adverse events							х

5 Sample Size

The sample size was based on the primary outcome, GLP-1 concentration after the Mixed Meal Tolerance Test.

The study was powered to detect a difference in peak of active GLP-1 of 10.0 pmol/L, equating to the previously estimated change in GLP-1 post-surgery in the Standard Limb RYGB group. The standard deviation of the change in outcome values was estimated to be

10.8 pmol/L within each group. It is calculated that, with a 5% significance level and 90% power, a sample size of 20 patients in each arm was required. Based on experience, it was estimated that up to 20% of patients will drop-out of the study. To allow for this, 25 patients in each arm of the trial were planned, 50 patients in total.

6 Study Objectives and Endpoints

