6.2 Demographic and Baseline measurements

The following demographic and baseline characteristics of the study participants will be collected:

- Age
- Gender
- Ethnicity
- Duration of T2DM
- Height

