9.2 Secondary Efficacy Analysis

Secondary outcomes measured on a continuous scale, with a baseline measurement, will be analysed using a similar approach to that outline for the primary efficacy outcome. The data from each post-operative timepoint will be analysed in a separate analysis.

For continuous secondary outcomes where there no baseline measurement, the two groups will be compared using the unpaired t-test. Alternatively, the Mann-Whitney test will be used if the assumptions of the t-test are not met.

For the continuous outcomes, the exceptions to the previously described methods are for the blood, urine and faecal microbial diversity and metabolomics outcomes. These will be analysed using non-metric multidimensional scaling (NMDS) plots. Additionally, PERMANOVA p-values will be generated using the UniFrac weighted distance matrix generated from Mothur. Family-level extended error bar plots will be generated, White's non-parametric t-test with Benjamini-Hochberg FDR will be utilised.

Binary and nominal outcomes (e.g. achieving diabetes remission) will be compared between the two study groups using either the Chi-square test, or Fisher's exact test if the number of responses in some categories is low.

Ordinal outcomes will be analysed using the Mann-Whitney test to allow for the natural ordering of the response categories.

The secondary efficacy analyses will be performed using the Full Analysis Population.

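### King's score and comorbidities are recorded at screening, but Section 9.2 compares them at follow-up with no baseline term; adjusting would be a cheap, minor gain in precision

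*SAP*

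**What the plan says.** Section 9.2 sorts the secondary outcomes by scale.

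- **Continuous, with a baseline:** handled like the primary outcome, that is, ANCOVA with the baseline value as covariate (Section 9.1).
- **Binary and nominal:** "Binary and nominal outcomes (e.g. achieving diabetes remission) will be compared between the two study groups using either the Chi-square test", or Fisher's exact test where counts are low.
- **Ordinal:** "Ordinal outcomes will be analysed using the Mann-Whitney test to allow for the natural ordering of the response categories".

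Neither of the last two rules has a baseline term. Section 6.3.2 lists comorbidities, King's Obesity Staging Score and T2DM remission among the 12-month secondary endpoints. In Table 1 (Section 4.4.1) the row "Comorbidities and King's Score" is marked at screening and at 12 months, while the remission row is marked at 12 months only. Section 8.3 defines baseline as the last value before surgery. For King's score and comorbidities that is the screening value.

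**The concern.** Outcomes that the trial measures before and after surgery are treated differently according to their scale. BMI and blood pressure are adjusted for baseline; the staging score and comorbidities are not, and no reason is given. Where the screening value predicts the 12-month value, leaving it out discards information already collected.

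That matters somewhat more in a small trial. Section 4.3 describes 1:1 randomisation in a single stratum, so the design does nothing to balance baseline severity between arms. What is at stake is the precision of two secondary clinical comparisons, not the primary result.

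**Working it through.** **1. The plan's own figure.** Section 5 is the only power statement, and it concerns peak active GLP-1. It is "powered to detect a difference in peak of active GLP-1 of 10.0 pmol/L", with an SD of "10.8 pmol/L within each group", and concludes that "with a 5% significance level and 90% power, a sample size of 20 patients in each arm was required". The formula is n per arm = 2(z₁ + z₂)²(SD/difference)².

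- One-sided 5%: 2 × (1.645 + 1.282)² × 1.08² ≈ 19.98, so 20. This reproduces the plan.
- Two-sided 5%: 2 × (1.960 + 1.282)² × 1.08² ≈ 24.5, so 25.
- Dropout of 20%: 20/0.8 = 25 per arm.

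The unstated sidedness is a separate matter. Here the figure shows only that 20 to 25 patients per arm will be available, and that no power is stated for the ordinal or binary outcomes.

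**2. Why a baseline term helps.** For a continuous outcome with baseline correlation ρ, adjustment multiplies the residual variance by about 1 − ρ². That is 0.91, 0.75 and 0.51 at ρ = 0.3, 0.5 and 0.7. Grouping into categories weakens this.

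The standard error of a chance baseline difference is √(2/n) SD: √(2/25) = 0.28 and √(2/20) = 0.32. At ρ = 0.6 an imbalance of one standard error moves the unadjusted contrast by 0.6 × 0.28 = 0.17 to 0.6 × 0.32 = 0.19 SD. The unadjusted test's error rate already allows for this; adjustment removes it as noise.

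**3. Ordinal outcome, simulated.** The SAP gives no correlation, category distribution or effect size, so all of these are assumptions: correlated normal variables at baseline and 12 months, cut into four levels, with two-sided 5% tests.

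| n per arm, shift | ρ | Mann-Whitney | Rank ANCOVA |
|---|---|---|---|
| 22, 0.7 SD | 0.3 | 54% | 55% |
| 22, 0.7 SD | 0.5 | 53% | 61% |
| 22, 0.7 SD | 0.7 | 55% | 74% |
| 25, 0.8 SD | 0 | 72% | 71% |
| 25, 0.8 SD | 0.3 | 70% | 73% |
| 25, 0.8 SD | 0.5 | 71% | 80% |
| 25, 0.8 SD | 0.7 | 71% | 89% |
| 20, 0.8 SD | 0.3 | 64% | 67% |
| 20, 0.8 SD | 0.5 | 59% | 67% |
| 20, 0.8 SD | 0.7 | 60% | 80% |

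At 22 per arm the gains are about 2 (1 from the rounded figures), 8 and 19 points. Type I error is about 5% for both methods. A repeat run with quartile cut-points gave gains of the same size.

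**4. Binary comorbidity, simulated.** Assumptions: 22 per arm, 50% prevalence, 0.8 SD shift on the underlying scale. The adjusted analysis is a baseline-adjusted risk difference with robust (HC3) standard errors.

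| ρ | Chi-square | Adjusted |
|---|---|---|
| 0.3 | 52% | 51% |
| 0.6 | 51% | 54% |
| 0.8 | 50% | 64% |

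Chi-square type I error was 5.0 to 5.5%. A further run at ρ = 0.3, 0.5 and 0.7 gave gains over Chi-square of about −1, +1 and +8 points.

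**5. Remission.** Section 4.2.1 requires diagnosed T2DM, so remission status before surgery is the same for every patient. Adjusting for a constant gains nothing.

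**The case against.** The strongest reply is that Mann-Whitney, Chi-square and Fisher's exact test are standard, prespecified and valid under randomisation, that these outcomes are secondary in a trial powered on GLP-1, and that nothing in Section 9.2 is wrong or contradictory. All of that stands, and it limits the point to efficiency.

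The reply also stands on two details. The SAP never says that King's score is ordinal; if it is handled as a numeric score, Section 9.2 already gives it ANCOVA. Nor does it say whether comorbidities means presence at 12 months or resolution since screening. So it cannot be asserted that a patient who never had a condition is counted the same as one whose condition resolved.

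A reader might infer more than the documents support:

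- **That the unadjusted results are biased.** They are not. Chance imbalance is covered by the tests' error rates, and simulated type I error for Mann-Whitney is about 5%.
- **That remission has the same defect.** It has no baseline of its own. HbA1c is measured before surgery and "Duration of T2DM" is listed in Section 6.2, but adjusting for other predictors is a different proposal. The SAP's rule for continuous outcomes uses only each outcome's own baseline. Multi-covariate logistic models with 40 to 50 patients are a debatable choice.
- **That the binary gain is large.** Against Fisher's exact test (38% power at ρ = 0.6 and at 0.8), adjustment appears to add 54 − 38 = 16 and 64 − 38 = 26 points. But Fisher's simulated type I error is only about 2%. Moving to Chi-square alone recovers 51 − 38 = 13 and 50 − 38 = 12 of those points.
- **That no effect size is planned.** Section 8.2 gives frequencies and percentages. What Section 9.2 does not specify is a between-arm estimate with an interval.

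**Conclusion.** The point holds in a limited form. For King's score, if treated as ordinal, and for comorbidities, a baseline is collected and the planned tests do not use it. The cost is lost precision, not validity.

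For the ordinal score the loss is about 2 to 19 power points at correlations of 0.3 to 0.7 (22 per arm, 0.7 SD shift). For a binary comorbidity it is about nil at 0.3 to 0.5 and roughly 8 points at 0.7. There is nothing to gain if baseline and 12-month values are uncorrelated. Every one of these figures rests on assumed correlations, shifts and category distributions, because the SAP supplies none. The severity is minor: a cheap improvement, not the correction of an error.

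**What to change.** In Section 9.2:

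- **King's score:** state the scale on which it is analysed. If ordinal, compare the 12-month score adjusted for the screening score by rank ANCOVA, van Elteren's test or a proportional-odds model; name one.
- **Comorbidities:** state that 12-month status is compared. Adjust each comorbidity for, or stratify it by, its screening status, using a baseline-adjusted risk difference with 95% CI or the Cochran-Mantel-Haenszel method.
- **Planned unadjusted tests:** keep them as supportive analyses and as the prespecified fallback where cells are sparse.
- **T2DM remission:** keep the planned test. Adjustment for HbA1c or T2DM duration is optional.

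The cost is a few lines of SAP text and minor programming, with no new data. The downside is possible sparse cells or model instability with 40 to 50 patients: in simulation up to 0.7% of adjusted logistic fits failed outright and others gave convergence warnings. The fallback covers this.

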9.3 Sensitivity Efficacy Analysis

If the Per Protocol Population differs in its membership from the Full Analysis Population, the primary outcome will be additionally analysed using this population. The analysis methods will be equivalent to those described in Section 9.1.

If there is no difference between the Per Protocol Population and Full Analysis Population, no sensitivity analyses will be performed.

9.4 Other Analyses

An additional set of analyses will examine the association between the key primary and secondary efficacy outcomes measured on a continuous scale and the proportion of the common channel length to the total small bowel length. The analysis will be performed using Pearson correlation. Alternatively, Spearman's rank correlation will be used if the Pearson correlation assumptions (e.g. non-linear relationship, both variables non-normally distributed) are not met. For each outcome, a single analysis will be performed for all patients, combining the two study arms together.

10 Safety Analyses

The main safety outcome is the occurrence of adverse events (AEs). For each of the study groups, the number of adverse events in each group and per patient will be summarised. Specific details of the adverse events will be recorded in addition to the number of AEs that are serious and non-serious.

If it is deemed that there are sufficient occurrences of adverse events in total, a formal test of significance will be performed to compare AE occurrence at the patient level between study arms. Fisher's exact test will be used for this analysis. However, it is acknowledged that the study is unlikely to be powered to show a difference between groups for this endpoint.

11 Technical Details

The data analysis will be primary performed using the statistical software packages Stata (version 15.1), SPSS (version 20 or later), GraphPad PRISM (version 6 or later). Programs recording details of all data manipulation and data analyses will be produced and kept, so that the analyses can be externally inspected and, if necessary, re-run.

The exception is for the analysis of the blood, urine and faecal microbial diversity and metabolomics outcomes, which will be analysed using the Vegan library within the R statistical package and the Statistical Analysis of Metagenomic Profiles software package.

12 Summary of Changes to the Analysis Plan

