6.3 Endpoints

6.3.1 Primary outcome measure

The primary study endpoint is:

• Peak of active GLP-1 concentration after the mixed meal tolerance test 1-2 weeks after the surgery.

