9.1 Primary Efficacy Analysis

The primary endpoint of the study is the peak of active GLP-1 concentration at the early mechanistic post-op visit.

The analysis will be performed using Analysis of Covariance (ANCOVA). In the analysis, the peak of active GLP-1 concentration at the early mechanistic post-operative visit will be considered as the outcome measure, whilst baseline peak of active GLP-1 will be included as a covariate.

If the data does not meet the assumptions of the ANCOVA analysis (e.g. normally distributed residuals, homogeneity of variance), a data transformation of the outcome variable (e.g. log transformation) before analysis will be utilised to ensure that the assumptions are met.

The summary statistics for the outcome variable will be produced in accordance with section 8.2. The baseline adjusted difference in outcome values between groups will be reported, along with a corresponding 95% confidence interval.

The primary study analysis will be performed using the Full Analysis Population (see section 7.2.1).

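### Section 9.4 correlates outcomes with the common-channel proportion without the baseline values that 9.1 and 9.2 adjust for; adding them would gain power at almost no cost

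*SAP*

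**What the plan says.** SAP section 9.4 plans a further set of analyses of "the association between the key primary and secondary efficacy outcomes measured on a continuous scale and the proportion of the common channel length", expressed as a share of the whole small bowel. The method is stated as "The analysis will be performed using Pearson correlation". The fallback is also a two-variable method: "Alternatively, Spearman's rank correlation will be used if the Pearson correlation assumptions" fail. The arms are pooled: "For each outcome, a single analysis will be performed for all patients, combining the two study arms together". No covariate, partial correlation or change score is named.

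The main analyses treat these outcomes differently. Section 6.3.1 defines the primary endpoint as "Peak of active GLP-1 concentration after the mixed meal tolerance test 1-2 weeks after the surgery", and in section 9.1 "the peak of active GLP-1 concentration at the early mechanistic post-operative visit will be considered as the outcome measure" while "baseline peak of active GLP-1 will be included as a covariate". Section 9.2 extends this: "Secondary outcomes measured on a continuous scale, with a baseline measurement, will be analysed using a similar approach" to the primary one. It excepts the microbial diversity and metabolomics outcomes.

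Section 6.4 defines absolute and percentage changes from baseline, but 9.4 does not refer to them. Table 1 (section 4.4.1) schedules the meal-test and clamp measurements before surgery, so the baseline values will exist.

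**The concern.** An outcome that is baseline-adjusted when the arms are compared is left unadjusted when it is related to bowel anatomy. As written, 9.4 uses post-operative values that still contain the variation between patients present before surgery. That variation is noise for the question asked, and its removal is the usual reason for the covariate in 9.1.

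There is a second, smaller issue. Arm allocation is randomised, but total small bowel length, the denominator of the proportion, is the patient's own anatomy. If bowel length is related to the pre-operative level of an outcome, an unadjusted correlation can reflect that relation and be read as something the operation produced.

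At stake is the interpretation of a supplementary mechanistic analysis. The randomised comparison is not touched.

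**Working it through.** **Inputs.** Section 9.4 states no sample size or power of its own. Section 5 plans 50 patients and allows 20% drop-out, so 50 × 0.8 = 40 evaluable. The SAP does not give the following, so they are assumed:
- r, the true correlation of proportion and post-operative outcome: 0.3;
- ρ, the correlation of an outcome's baseline and post-operative values: 0 to 0.7;
- c, the correlation of the proportion with the baseline value: 0 for the power calculation.

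**Power.** With c = 0, the correlation given baseline is r/√(1 − ρ²). By Fisher's z at two-sided 5%, power ≈ Φ(atanh(r)·√(n − 3) − 1.96) unadjusted. Adjusted, r/√(1 − ρ²) replaces r and n − 4 replaces n − 3.

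- Unadjusted, n = 40: atanh(0.3) = 0.3095; × √37 = 1.883; power Φ(−0.077) = 47%.
- Adjusted, ρ = 0.5: 0.3/√0.75 = 0.346; atanh = 0.361; × √36 = 2.168; power Φ(0.208) = 58%.

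| ρ | correlation given baseline | power, n = 40 | power, n = 50 |
|---|---|---|---|
| unadjusted | 0.300 | 47% | 56% |
| 0 | 0.300 | 46% | 56% |
| 0.3 | 0.314 | 50% | 60% |
| 0.5 | 0.346 | 58% | 69% |
| 0.7 | 0.420 | 77% | 86% |

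At n = 40 the gain is about 3, 11 and 30 points at ρ = 0.3, 0.5 and 0.7. At ρ = 0 there is a loss of about 1 point, the price of the degree of freedom.

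**Association present before surgery.** If the proportion has no relation to the outcome given baseline, the marginal correlation is c·ρ. The size of c depends on how much of the proportion's spread is anatomy rather than allocation. Section 2 of the SAP's text (the introduction) gives biliopancreatic limbs of 150 and 50 cm, a randomised difference of 100 cm.

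Take the proportion as 1 − (biliopancreatic + alimentary limb)/total length. Assume a mean total length of 500-700 cm, an SD of 80-150 cm and an alimentary limb of 75-150 cm, equal in both arms. Arm then explains roughly 35-84% of the proportion's variance. If bowel length correlates 0.2 with baseline (assumed), c is at most about 0.2 × √(1 − arm share):
- share 84%: 0.2 × √0.16 = 0.08;
- share 35%: 0.2 × √0.65 = 0.16.

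Rejection of the unadjusted test at nominal 5%, n = 40, by Fisher's z:
- lowest case, c = 0.08 and ρ = 0.3: marginal correlation 0.024, rejection about 5%;
- highest case, c = 0.16 and ρ = 0.7: marginal correlation 0.112, rejection about 10%.

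In simulation (20,000 runs per setting) the partial correlation given baseline rejects in about 5% throughout.

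**The case against.** **9.4 may intend change scores.** Section 6.1 words the primary objective as a change, section 6.4 defines changes, and no analysis in section 9 names them. Since 9.4 does not say which value it uses, change scores are possible. But it refers to the outcomes, and 6.3.1 and 9.1 define the primary one as the post-operative peak. Even on the other reading the section needs a sentence, and a change score does not in general remove dependence on baseline. What stands is that the power figures above apply to post-operative values only.

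**The false-positive risk can be overstated.** A reader might infer badly inflated error: with c set directly at 0.2-0.3, simulated rejection at n = 40 is 9-15% at ρ = 0.5 and 14-26% at ρ = 0.7. The document does not support those values of c. Because allocation drives much of the proportion's spread, c = 0.2 would need bowel length itself to correlate at least 0.2/√0.65 = 0.25 to 0.2/√0.16 = 0.50 with baseline, and c = 0.3 at least 0.37 to 0.75. Nothing in the SAP suggests this. Nor is such a rejection an error for the stated aim, which is association: a marginal association would then really exist. It misleads only if read as an effect of the operation.

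**The analysis is minor.** A reader might take 9.4 as the plan's decisive test of whether anatomy explains the effect. The SAP presents it as additional, and no primary or secondary conclusion rests on it. A simple correlation is a common choice for such work.

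**The fix is partial.** It does not address the pooling of arms without an arm term, which is a separate and larger weakness of 9.4, nor other patient-level confounding of bowel length. This is true, but it is no reason to leave out a covariate already in hand.

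**Conclusion.** The point holds as a free improvement. Section 9.4 specifies a method with no baseline term for outcomes that 9.1 and 9.2 baseline-adjust, and nothing elsewhere in the SAP supplies the adjustment. The main consequence is lost power, whose size rests wholly on the assumed ρ: negligible if baseline is weakly prognostic, about 11 points at ρ = 0.5 and about 30 at ρ = 0.7 (n = 40, r = 0.3). The possible carry-over of an association present before surgery is secondary: about 5-10% rejection on the assumed bowel lengths and a bowel length-baseline correlation of 0.2.

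The point does not reach outcomes without a baseline, the microbial and metabolomic outcomes that 9.2 excepts, or outcomes already relative to baseline such as percentage total body weight loss. It leaves the primary result unaffected.

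**What to change.** Add to section 9.4: for each continuous outcome with a pre-operative value, the association will be estimated from a linear model of the post-operative value on the common-channel proportion and that outcome's baseline value, or by the equivalent partial correlation, using ranks where Spearman would have applied. The slope or partial correlation will be reported with its 95% confidence interval. The simple correlation is kept for outcomes with no baseline and for those already expressed relative to baseline, such as percentage total body weight loss.

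The cost is a sentence or two of SAP text and one residual degree of freedom per model. No new data are needed, since 9.1 and 9.2 already use these baseline values.

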The most effective and durable treatment for both obesity and type 2 diabetes mellitus (T2DM) remains bariatric surgery. Alternative surgical techniques have been sought to improve the rates of T2DM remission. Standard Limb RYGB and biliopancreatic diversion (BPD) has been showed to lead to a matched total body weight loss of 33% at 2 years post-operatively. Unfortunately, the BPD procedure has the distinct disadvantage of a substantially higher risk of developing severe nutritional complications, and this has limited its use.

To improve the glucose-lowering efficacy of Standard Limb RYGB, whilst avoiding the high risk of complications with the BPD procedure, the Long Limb RYGB has been devised as a hybrid operation that combines the standard design of Standard Limb RYGB, but with a longer biliopancreatic limb. Previous research has suggested that the rates of any complications, including nutritional, were not higher than those reported after Standard Limb RYGB.

The main anatomical difference between Long Limb RYGB and Standard Limb RYGB is that the segment of the bypassed proximal intestine, the biliopancreatic limb, is longer (150 vs. 50cm respectively). This means that in the Long Limb RYGB the common channel is shorter, and as a result nutrients reach the distal small bowel faster and in a less-digested state. The hypothesis is that the Long Limb RYGB is better for treatment of T2DM because: a) It increases post-prandial secretion of gut hormones, and in particular glucagon-like peptide-1 (GLP-1) which results in the immediate post-prandial insulin secretion significantly higher than the Standard Limb RYGB.

b) It increases insulin sensitivity significantly more than the Standard Limb RYGB, before and after weight loss has taken place.

The trial will evaluate the efficacy on T2DM of the Long Limb RYGB compared to the Standard Limb RYGB, and investigate the mechanisms underlying any potential differences by conducting:

- 1. Mechanistic assessments with Mixed Meal Tolerance Test (MMTT) and Hyperinsulinaemic Euglycaemic Clamp at: pre-operative, early mechanistic postoperative (at 1-2 weeks after the surgery) and late mechanistic post-operative visits (at 20% total body weight loss after the surgery).
- 2. Clinical assessment pre-operatively, at the day of surgery and at 3, 6 and 12 months post-operatively.

4 Study Methods

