4.3 Randomisation and Blinding

Participants were randomised to Long Limb or Standard Limb RYGB surgery in a 1:1 ratio. All patients were randomised in a single stratum.

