6.3.2 Secondary outcome measures

The secondary endpoints are measured at several different timepoints.

Endpoints from mixed meal test at late mechanistic post-operative visit:

• Peak of active GLP-1 concentration

Endpoints from both early and late mechanistic post-operative visits:

- a) From the Hyperinsulinaemic Euglycaemic Clamp
 - Rate of glucose appearance (Ra) and disposal (Rd) and metabolic clearance rate of glucose (MCR) basal, low and high
- b) From the MMTT:
 - Active GLP-1 concentration (AUC)
 - Total GLP-1 (peak, AUC)
 - PYY (peak, AUC)
 - GIP (peak, AUC)
 - Markers of insulin secretion (peak, AUC)
 - Plasma glucose (peak, AUC)
 - Bile acids (peak, AUC)
 - FGF-19 and 21 (peak, AUC)
 - Systolic and diastolic blood pressure (AUC)
 - Heart rate (AUC)
 - Appetite ratings (Visual Analogue Scales; AUC)
- c) Blood, urine and faecal microbial diversity and metabolomics
- d) Total caloric intake and macronutrient composition % fat, % protein, % carbohydrates
- e) Body composition and Basic Metabolic Rate (BMR)

Endpoints at the day of surgery:

- Common channel length
- Total small bowel length
- Proportion of common channel to total small bowel length
- Operating time
- Length of in hospital stay

Endpoints at 3, 6 and 12 months:

- HbA1c
- % of total body weight loss
- Number of glucose lowering medications

Secondary endpoints at 12 months:

- % of total body weight loss
- BMI
- Body composition
- Basic Metabolic Rate (BMR)
- Waist, hips and neck measurements
- T2DM remission
- Comorbidities
- Medications
- King's Obesity Staging Score
- Systolic and diastolic blood pressure
- Heart rate
- Oxygen saturation
- Bowel movements frequency

- Blood tests: fasting plasma lipids concentration, fasting plasma glucose, haematinics, vitamins
- Total caloric intake
- Macronutrient composition % fat, % protein, % carbohydrates
- Faecal caloric content

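### The pooled correlation with common-channel proportion (SAP 9.4) cannot separate a graded channel-length relation from the difference between the arms; an arm-adjusted estimate should be added

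*SAP*

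**What the plan says.** Section 9.4 (Other Analyses) relates the key continuous primary and secondary outcomes to "the proportion of the common channel length to the total small bowel length". On method it says: "The analysis will be performed using Pearson correlation", with Spearman's rank correlation as the fallback. On the sample it says: "For each outcome, a single analysis will be performed for all patients, combining the two study arms together". It plans no arm covariate, partial correlation or within-arm analysis, and no other section of the SAP adds one.

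The background text before section 4 describes how the operations differ: "the biliopancreatic limb, is longer (150 vs. 50cm respectively". It then states the consequence: "This means that in the Long Limb RYGB the common channel is shorter".

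Section 6.3.2 lists "Total small bowel length" and "Proportion of common channel to total small bowel length" as separate day-of-surgery endpoints, so the denominator is measured for each patient. Section 4.3 gives 1:1 allocation.

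**The concern.** Arm moves the exposure by design, and the trial's hypothesis is that arm also moves the outcomes. When both hold, pooling the arms produces a correlation even if patients with a smaller proportion do no better or worse than others who had the same operation. Part of the pooled coefficient then repeats the between-arm comparisons of sections 9.1 and 9.2.

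This matters because the background text sets out to investigate the mechanisms behind any difference between the operations. A reader will naturally ask whether the remaining bowel fraction matters beyond which operation was done. The planned correlation cannot answer that, and the patient-to-patient variation that could help is mixed with the arm contrast. Changing from Pearson to Spearman does not address this.

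**Working it through.** **The plan's own figure.** Section 9.4 gives no figure for the correlation. The effect size used here comes from section 5: difference 10.0 pmol/L, SD 10.8, 5% level, 90% power, 20 per arm. The normal formula gives 2 × [10.8 × (1.645 + 1.282)/10]² ≈ 20 with a one-sided 5% test, which matches. A two-sided test gives 24.5, i.e. 25. Allowing for 20% dropout, 20/0.8 = 25 per arm, as stated. This point does not depend on sidedness.

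**Inputs.**
- From the SAP: biliopancreatic limb 50 or 150 cm; 1:1 allocation; 20 evaluable per arm; arm effect 10 pmol/L; SD 10.8.
- Assumed, because the SAP does not give them: total small bowel length L with mean 500, 600 or 700 cm and SD 60, 100 or 150 cm; alimentary limb 100 cm in both arms.

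**Formula.** Proportion P = (L − 100 − B)/L, with B = 50 (Standard) or 150 (Long). At a given L the arms differ by 100/L.

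**Hand check, central case (L mean 600, SD 100).**
- Arm gap in P: 100/600 = 0.167. Between-arm variance: (0.167/2)² = 0.0069.
- Within-arm SD of P is about (100 + B)/L² × SD(L): 150/600² × 100 = 0.042 (Standard) and 250/600² × 100 = 0.069 (Long). Mean within-arm variance: (0.0017 + 0.0048)/2 = 0.0033.
- Share of variance in P due to arm: 0.0069/(0.0069 + 0.0033) ≈ 0.68.
- Correlation of arm with outcome at d = 10/10.8 = 0.926: 0.926/√(0.926² + 4) = 0.42.
- Expected pooled r with no within-arm relation: −√0.68 × 0.42 ≈ −0.35. The two-sided 5% threshold with 40 patients is |r| = 2.024/√(2.024² + 38) = 0.31, so rather more than half of trials should cross it.

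**Simulation.** 20,000 trials per scenario; outcome = arm effect + N(0, 10.8), with no relation to P within arm; two-sided 5% tests.

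| L mean / SD (cm) | Share of P variance due to arm | Pooled Pearson significant: 10 pmol/L | 5 pmol/L | 0 |
|---|---|---|---|---|
| 500 / 60 | 80% | 70% | 24% | 5% |
| 500 / 100 | 58% | 55% | 19% | 5% |
| 500 / 150 | 43% | 42% | 15% | 5% |
| 600 / 60 | 85% | 74% | 26% | 5% |
| 600 / 100 | 66% | 61% | 21% | 5% |
| 600 / 150 | 45% | 43% | 15% | 5% |
| 700 / 60 | 89% | 77% | 27% | 5% |
| 700 / 100 | 73% | 67% | 22% | 5% |
| 700 / 150 | 51% | 49% | 17% | 5% |

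The mean pooled r in the central case is −0.34, close to the hand check. At 10 pmol/L, Spearman is significant in 45–67% of trials. Adjusted for arm (correlation after centring both variables within arm), the rate is about 5% in every row. Letting the common alimentary limb also vary from 75 to 150 cm widens the 10 pmol/L range to 37–77% and the variance share to 38–91%.

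**Cost of adjusting.** In a second set of runs P itself drives the outcome, scaled to give the same 10 pmol/L arm difference. At mean 600 cm:

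| SD of L (cm) | Power, pooled | Power, arm-adjusted |
|---|---|---|
| 60 | 87% | 22% |
| 100 | 93% | 53% |
| 150 | 98% | 85% |

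**The case against.** **The pooled correlation is a real association.** The background text proposes that the longer limb works through the shorter common channel. On that view the between-arm variation in the proportion is randomised variation in the proposed mechanism, not a nuisance. Section 9.4 speaks only of an association, under Other Analyses, and never claims a dose-response or evidence independent of arm. This stands. The fault lies in what the analysis can be made to show, since the plan offers nothing to separate the two readings.

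**Stronger readings go too far.** A reader might infer that limb length fixes the proportion. It does not: section 6.3.2 records total small bowel length for each patient, and that also determines the ratio. A reader might infer that the correlation mostly re-measures the arm effect. That depends on the spread of bowel length, which the SAP does not give; in the table the arm share falls below half in two of the three rows with SD 150 cm. A reader might also infer that a spurious finding is likely. That holds only if the outcome has a sizeable arm effect that does not act through the proportion. With no arm effect the pooled test keeps its 5% level, and section 9.4 covers many outcomes for which the primary design effect need not apply.

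**Adjustment is costly.** This also stands, as the second table shows. It argues for adding the adjusted estimate rather than replacing the pooled one. With limb lengths set by the operation, within-arm variation in the proportion comes from bowel length, which is not randomised, so the adjusted slope is itself observational.

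**Conclusion.** The point holds in a limited form. As written, section 9.4 cannot distinguish a graded relation with common-channel proportion from the difference between the arms, and nothing else in the SAP can. This follows from the SAP's own text and needs no assumed figure.

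The size does rest on assumptions. For the bowel lengths tabulated, with no within-arm relation, the pooled test is significant in about 42–77% of trials at the design effect (about 61% in the central case), 15–27% at half of it, and 5% with no arm effect, against about 5% after adjustment for arm.

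The documents do not support saying that the pooled result is invalid as a marginal association, that it will probably mislead for every outcome, or that the sponsor plans to present it as a dose-response. The primary and secondary between-arm comparisons are untouched. It is an inexpensive improvement to a supplementary analysis.

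**What to change.** In section 9.4, for each outcome:

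- Add a linear model of the outcome on common-channel proportion and arm, plus the baseline value where one is measured (or the partial correlation given arm). Report the within-arm slope with its 95% CI beside the pooled correlation.
- Plot the scatter with the arms marked.
- State that any claim of a channel-length relation beyond the arm difference will rest on the arm-adjusted estimate, and describe the pooled correlation as a marginal association that includes the arm effect.
- State that the adjusted slope will be judged by its confidence interval, and that a non-significant slope will not be read as no channel-length effect.

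The cost is a change of SAP wording; all variables are already collected. The statistical price is the lower precision shown in the working, which is why the pooled correlation should stay.
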